The specific aims of this pilot study are: **Aim 1)** *To identify whether no prep ready to eat meals (intervention) or ingredient bundles (control) have higher client acceptability, liking, satisfaction, and perceived diet quality ratings.* **Hypothesis:** No prep ready to eat meals will have higher client acceptability, liking, satisfaction, and perceived diet quality scores than ingredient bundles. **Rationale:** Previous research has shown that acceptance, liking, satisfaction, and perceived diet quality are important determinants of the foods people are willing to eat and the ultimate success of diet-related interventions¹². Aim 1 will establish which strategy is most acceptable and desirable for food pantry clients to inform the development of a future randomized-controlled trial that will aim to test which strategy is most effective at improving objective dietary quality and reducing health-related risk factors. **Aim 2)** *To identify whether no prep ready to eat meals (intervention) or ingredient bundles (control) have higher feasibility ratings with food pantry staff.* **Hypothesis:** No prep ready to eat meals will have higher feasibility ratings than ingredient bundles among pantry staff. **Rationale:** It's unclear how much staff time and pantry resources are needed to put together an ingredient bundle from a recipe or store no prep ready to eat meals in appropriate refrigeration units. This pilot study will determine the resources needed to carry out each program and determine which is preferable and feasible for the pantry staff that would be asked to carry out either model given that staff buy-in is a key component to intervention success¹³.

2. Background.

- Describe past experimental and/or clinical findings leading to the formulation of your study.
- For research involving investigational drugs, describe the previously conducted animal and human studies.
- For research that involves FDA approved drugs or devices, describe the FDA approved uses of this drug/device in relation to your protocol.
- Attach a copy of the approved labeling as a product package insert or from the Physician's Desk Reference.

You may reference sponsor's full protocol or grant application (section number and/or title) or if none, ensure background includes references.

Please respond to all components of this item, or clearly indicate which components are not applicable.

a. Background

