To test the second hypothesis, I will use a mixed-methods approach with food pantry staff (N=10), including questionnaires with fixed and open-ended items on feasibility and satisfaction of each distribution strategy followed by 30-minute semi-structured 1-1 interviews conducted by UT Southwestern study staff.

4. Research Plan / Description of the Research Methods:

4.a. Provide a comprehensive narrative describing the research methods.

- 1) Provide the **order in which tests/procedures will be performed**,
- 2) Provide the **setting** for these events and a description of the **methods used to protect privacy** during the study.
- 3) Provide the **plan for data analysis** (include as applicable the **sample size calculation**)

Please respond to all components of this item, or clearly indicate which components are not applicable.

C.1.5 Intervention Methods

After completing consent forms, participants will be randomized to receive no prep ready-to-eat meals or ingredient bundles using random number generation. Participants will be unaware of their assignment until they are asked to select study meals, in which case it will be obvious because of the food items available to select. Participants will complete questionnaires and then select meals – they can select up to 2-meals, or the bundles needed to make 2-meals, for 14-days for themselves and 2 additional members of their household. Participants will elect to receive one week of meals after selection and come back to pick-up the second week of meals or they will take home all study meals at one time (participants choice). Participants will return at the end of the 2-week study period to complete the follow-up questionnaires and receive payment. A study timeline of intervention components and data collection is provided in **Table 1** to aid visualization of the study plan and timeline for **food pantry clients**.

Table 1. Study plan and timeline for food pantry clients.

Baseline appointment (Day 0)	Intervention (Day 1 - Day 14)	Follow-up appointment (Day 15)

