Food pantry staff will answer feasibility items for each of the intervention groups, such as desire to implement each food distribution strategy in the future, perceived appropriateness of the intervention given their organizational goals, perceived sustainability, and financial/staff resources needed to carry out the intervention longer term³². Staff participants will also respond to qualitative open-ended response items such as "Describe any challenges experienced with distributing ingredient bundles" "Describe any challenges experienced with distributing no prep ready-to-eat meals". Responses to the questionnaire will be followed with 30-minute semi-structured 1-1 interviews with study personnel, which give pantry staff the opportunity to directly voice any challenges or preferences that come up when implementing either approach. The pantry personnel perspective will allow us to design a feasible and sustainable longer-term intervention.

C.1.7. Analytic Plan

C.1.7.1. Analytic Plan for Pantry Client Data

Descriptive statistics (e.g., means, percentages, chi-squared tests of independence) will be used to describe participant characteristics and baseline differences. The independent variable of interest will be randomized group assignment (e.g., no prep ready to-eat-meals vs. ingredient bundles). Spearman's correlation and/or repeated measures Analysis of Variance (ANOVA) will be used to describe the association between group assignment and client's perceived diet quality at follow-up. If normally distributed, repeated-measures ANOVA is acceptable and will be used. If non-normal, Spearman's correlation will be used. For the other three outcomes of interest (satisfaction, acceptability, and liking) sum scores will be calculated, and model assumptions will be tested (e.g. residual distributions) before proceeding with repeated-measures Analysis of Variance (ANOVA) to test for group effects on study outcomes of interest and group-by-time interactions.

C.1.7.2 Analytic Plan for Pantry Staff Data

Descriptive statistics (e.g., means, percentages) will be used to describe quantitative items on staff feasibility and satisfaction. Qualitative thematic analysis of open-ended questionnaires and interviews will be synthesized into key findings and suggestions for future intervention development.

Form A

IRB # **STU 2022-0809**

4.b. List of the study intervention(s) being tested or evaluated under this protocol

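### Aim 2 hypothesises higher staff feasibility ratings for ready-to-eat meals, but the staff analysis plans no between-strategy difference and no measure of its uncertainty

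*Combined protocol and SAP*

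**What the plan says.** The Aim 2 objective in the specific aims is comparative: it asks which strategy will "have higher feasibility ratings with food pantry staff". The hypothesis gives a direction: "No prep ready to eat meals will have higher feasibility ratings than ingredient bundles among pantry staff". The rationale says the pilot will "determine which is preferable and feasible for the pantry staff that would be asked to carry out either model".

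Section 3 (Study Design) describes the staff component with the words "To test the second hypothesis, I will use a mixed-methods approach with food pantry staff (N=10" and lists "questionnaires with fixed and open-ended items on feasibility and satisfaction of each distribution strategy", followed by individual interviews.

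Section C.1.6.2 (Pantry Staff Measures) says "Food pantry staff will answer feasibility items for each of the intervention groups". It gives examples of item topics but no response scale, no number of items and no feasibility score.

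Section C.1.7.2 (Analytic Plan for Pantry Staff Data) has two sentences. The quantitative one is "Descriptive statistics (e.g., means, percentages) will be used to describe quantitative items on staff feasibility and satisfaction". The qualitative one is "Qualitative thematic analysis of open-ended questionnaires and interviews will be synthesized into key findings and suggestions for future intervention development". No other section adds a staff comparison, interval, test or decision rule. The client plan in C.1.7.1, by contrast, does name an analysis of group effects.

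**The concern.** The aim, the hypothesis and the Study Design section all promise a comparison of ratings. The analysis section promises a description of items. The missing step is the one that turns ratings of two strategies into a statement about which is rated higher, and how firmly.

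The staff result is meant to inform which model staff prefer and could sustain in a later intervention. With 10 raters, two means can differ by chance alone. If only those means are reported, a reader can see their order but cannot tell a consistent preference from a small difference within the noise. Interviews can explain why staff prefer one model, but they do not give the size or uncertainty of a rating difference, which is what the hypothesis is about.

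**Working it through.** **Inputs from the documents.** Staff sample: 10 (Study Design). Both strategies covered by the items (Study Design and C.1.6.2), which implies two ratings per person. The documents give no SD, response scale, confidence level or effect size for staff ratings, so there is no stated figure to reproduce. I take 95% confidence as an assumption and express widths in SD units.

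**Step 1: what the planned summaries give.** If every staff member answers both versions of an item, subtracting the two means gives the mean within-person difference. So the direction and the point estimate can be read from means by strategy. The uncertainty, and the number of staff who favour each strategy, cannot.

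**Step 2: width of the interval that is missing.** For *n* pairs, the half-width of the 95% paired t interval, in units of the SD of the differences, is t(0.975, *n* − 1) / √*n*.

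| Complete pairs | Half-width (SD of differences) |
|---|---|
| 10 | 2.262 / 3.162 = 0.72 |
| 9 | 0.77 |
| 8 | 0.84 |

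For scale only: if the SD of the differences were 0.5, 1.0 or 1.5 points (an assumption), the half-width with 10 pairs would be 0.36, 0.72 or 1.07 points.

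**Step 3: why means and SDs by strategy do not give this width.** With equal rating SDs for the two strategies (assumed) and within-person correlation ρ, the SD of the differences is √(2(1 − ρ)) rating SDs. With 10 pairs the half-width is therefore 2.262 × √(2(1 − ρ)/10) rating SDs.

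| ρ | Half-width (rating SD) |
|---|---|
| 0 | 1.01 |
| 0.5 | 0.72 |
| 0.8 | 0.45 |

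The same two means and SDs are compatible with intervals that differ by a factor of 1.01/0.45, about 2.2. The correlation appears only if the differences are formed within person.

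**Step 4: the same point in counts.** Suppose 8 of 10 staff rated ready-to-eat meals higher on an item, with no ties. The exact (Clopper-Pearson) 95% interval for that proportion runs from 44% to 97.5%, so it includes an even split. With 9 of 10 it runs from 55.5% to 99.7%. A clear majority among 10 raters can still be weak evidence, and the reader needs the counts to see this.

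**The case against.** The strongest reply is that this is a pilot with 10 staff and a mixed-methods design, and that descriptive statistics with interview themes are a reasonable way to learn from so few people. The list of descriptive statistics is open, items are collected for each strategy, and side-by-side summaries are plainly intended. No client result depends on the staff analysis. The documents also do not say whether the 10 are a sample or all the relevant staff at the pantry. If they are all of them, the observed means answer the question for that pantry, and a sampling interval adds little.

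Much of this stands. Descriptive analysis is defensible here, and the absence of a significance test is not a fault. The remark about a complete staff group is fair too, although the counts and within-person differences would still be the direct answer to Aim 2, and the result is meant to guide a later intervention. What the reply does not remove is the mismatch: an open list leaves room for a difference with its uncertainty but commits to neither, while the Study Design section says the hypothesis is tested.

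Two stronger readings are tempting. A reader might infer that the plan cannot speak to Aim 2 at all. The documents do not support that, because means by strategy are implied and would show direction. A reader might also infer that, with several feasibility items, one is likely to favour ready-to-eat meals by chance and be taken as proof. The documents list item topics only as examples, fix no number of items, and nowhere propose to draw the conclusion from a single item, so no such error rate can be derived from them.

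**Conclusion.** The concern holds as a mismatch between a directional hypothesis said to be tested and an analysis that names neither the difference nor its uncertainty. With 10 complete pairs the unreported 95% half-width is 0.72 SD of the within-person differences, rising to 0.84 if only 8 staff complete both ratings. It cannot be reconstructed from summaries by strategy.

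The textual finding needs no assumption beyond reading the sections together. The widths assume 95% confidence and paired ratings, which the documents imply but do not state; the widths in rating SDs also assume equal SDs. Any figure in scale points rests on assumed SDs. The change should be made because it uses data already planned, but the gap is confined to Aim 2 and does not touch the randomised client comparison.

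**What to change.** In C.1.6.2, state that each staff member rates both strategies on the same fixed items.

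In C.1.7.2, add text such as: *For every fixed feasibility item, the within-person difference (ready-to-eat meals minus bundles) will be reported as a mean with a 95% paired interval, together with the number of staff rating ready-to-eat meals higher, equal or lower. This is estimation only. No hypothesis test will be done, and no conclusion will be drawn from any single item.*

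In Study Design, replace the statement that the second hypothesis will be tested with one that the difference will be estimated. If no comparison is wanted, reword Aim 2 and its hypothesis as descriptive instead; that costs nothing but gives up the claim that one strategy is rated higher.

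The first option costs a few lines of analysis, with no extra staff, clients or visits. Its limits should be stated: the intervals will be wide, they apply to staff at one pantry, and item-by-item reporting gives no single Aim 2 number unless the items share a response scale that allows a total.
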